10.7.6. Non-ICH Listings

Non-ICH: Listings					
No.	Population	IDSL / TST ID / Example Shell	Title	Programming Notes	Deliverable [Priority]
22	Analysis		Listing of GI- VAS		SAC
23	Analysis		Listing of MSAQ		SAC
24	Analysis		Listing of MRI		SAC

11. ATTACHMENTS [DOCUMENTATION FROM MARTINOS]

11.1. Reporting & Analysis Plan for Imaging Data for Part A

11.1.1. Overview of Quality Control for Imaging Data

Quality control procedures will include visual inspection of raw brain images for presence of various artifacts, including but not limited to, aliasing, excessive distortion, Nyquist N/2 ghosting, and signal inhomogeneities. We will also assess head motion correction parameters to ensure that subjects were not moving excessively during the functional MRI (BOLD fMRI and pCASL) scans. We will evaluate 1) total translation and rotation motion, 2) relative TR-to-TR motion, 3) number of relative translations (> 0.1 mm). For pCASL data, we will calculate rCBF and ensure values within the gray matter are within normal bounds (40-60 mm/100 g tissue/min). For ¹H-MRS data we will assess spectra to ensure adequate SNR (Cramer–Rao lower bounds values below 40%).

We will perform single-subject level analyses and include data from (1) resting-state BOLD fMRI, (2) pseudo-continuous arterial spin labelling (pCASL), and (3) proton-density weighted magnetic resonance spectroscopy (¹H-MRS).

Primary Outcomes/Endpoints:

1. Resting-state functional connectivity (resting-state BOLD fMRI)
2. Regional cerebral blood flow (rCBF) (pCASL)
3. Glutamine/Glutamate (Glx) and GABA concentrations (¹H-MRS)

1. Resting-state fMRI (rs-fMRI)

Resting-state BOLD signal MRI data collected at off-therapy and exenatide post-dose MRI scan sessions will be analyzed using a whole-brain seed-to-voxel approach. The seed-to-voxel driven approach will include *a priori* seed ROIs placed in brain areas subserving nausea-related processing including regions identified from our prior study ([name] et al. Cereb Ctx 2013). These regions will include: interoceptive/sensory (insula, dACC), emotional/affective (amygdala, pgACC), and cognitive/evaluative (dlPFC/OFC) brain areas, primary visual (V1) and extrastriate cortices (area MT+/V5). Group analyses will be performed using a paired t-test (off-therapy vs. exenatide) with FSL's FLAME (FMRIB's Local Analysis of Mixed Effects).

2. pCASL

pCASL data will be analysed to assess regional cerebral blood flow (rCBF) within the brain during off-therapy relative to exenatide post-dose MRI scans. Quality control of imaging data will be performed by visual inspection with adequate data denoted by mean rCBF values over the gray matter within a previously defined normal range (i.e., 40-60 mm/100 g tissue/min). In addition, all data will undergo motion and physiological noise

correction. These rCBF maps will be calculated for each subject and each scan at the single subject-level.

3. ¹H-MRS

Magnetic resonance spectroscopy (¹H-MRS) analysis will assess regional differences in glutamine/glutamate (Glx) and GABA concentrations, normalized as a ratio with creatine. MRS quantification of metabolites of interest will be based on frequency domain analysis using a Linear Combination of Model spectra (LCModel). Cramer–Rao lower bounds (CRLBs), as reported from the LCModel analysis, will be used to assess the reliability of the major metabolites and adequate SNR. CRLBs values less than 40% will be further analyzed. Metabolite maps for each subject, and each session will be calculated.

Secondary outcomes/endpoints:

Additional analyses will be conducted for secondary outcome measures including heart rate, heart rate variability, respiratory rate, ECG intervals, blood pressure, and skin conductance level. Electrogastrogram (EGG) data will also be analysed as a secondary exploratory outcome. We will provide clean, processed physiological data in the subject/scan directories when available (secondary ANS data will not be available from every scan due to MR-induced artifacts).

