2. SUMMARY OF KEY PROTOCOL INFORMATION

2.1. Changes to the Protocol Defined Statistical Analysis Plan

Since the study was terminated early; Part B was cancelled prior to the completion of Part A, 4 subjects completed Part A as planned and a decision was made to not complete group analysis of the 4 subjects. Therefore, no interim analyses will be performed as stated in the originally planned statistical analysis specified in the protocol / protocol amendment 1 [(Dated: 28/Nov/2016)].

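### The imaging plan in SAP Attachment 11 omits the albiglutide session from resting-state BOLD and specifies a group t-test that SAP 2.1 appears to exclude, with no reason given for either

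*SAP*

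**What the plan says.** SAP 1 and SAP 2.2 both give the primary objective as the effect of albiglutide compared with exenatide on nausea-related brain activity and connectivity. The four primary endpoints are resting-state BOLD, regional cerebral blood flow, glutamate and GABA. SAP 1 says the primary analyses will be summary outputs and listings covering all four, with no restriction to one drug. SAP 7 refers the reader to Attachment 11 for the detail.

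SAP 2.1, the section for changes from the protocol analysis, reports that Part B was cancelled, that four subjects completed Part A as planned, and that "a decision was made to not complete group analysis of the 4 subjects". It then concludes that no interim analyses will be done.

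Attachment 11 (SAP 11.1.1) contains the following:

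- **Level of analysis:** "We will perform single-subject level analyses and include data from (1) resting-state BOLD fMRI", followed by pCASL and MRS.
- **BOLD sessions:** "Resting-state BOLD signal MRI data collected at off-therapy and exenatide post-dose MRI scan sessions will be analyzed", by a whole-brain seed-to-voxel method with a priori seeds. "These regions will include: interoceptive/sensory (insula, dACC), emotional/affective (amygdala, pgACC), and cognitive/evaluative (dlPFC/OFC) brain areas", plus visual areas.
- **BOLD group test:** "Group analyses will be performed using a paired t-test (off-therapy vs. exenatide", run in FSL's FLAME.
- **pCASL:** blood flow is assessed "within the brain during off-therapy relative to exenatide post-dose MRI scans", but also "These rCBF maps will be calculated for each subject and each scan at the single subject-level".
- **MRS:** the "analysis will assess regional differences in glutamine/glutamate (Glx) and GABA concentrations, normalized as a ratio with creatine". No treatment is named, and metabolite maps are made for every subject and session.

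**The concern.** There are two separate problems.

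First, a programmer or report author cannot tell whether a group test on four subjects is to be run. SAP 2.1 says group analysis will not be completed, and Attachment 11 opens at the single-subject level but then prescribes a group test. Whether that test is reported would be settled outside the plan.

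Second, the one place that defines the primary imaging analyses drops one of the two drugs from a primary endpoint, while the objective still compares the two. Followed literally, the plan yields no albiglutide BOLD result, so for that endpoint the objective cannot be addressed even descriptively. For pCASL the stated comparison also involves exenatide alone. A reader of the final report would see exenatide against off-therapy with no explanation of what happened to albiglutide.

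**Working it through.** This is a consistency check. The documents state no figure that needs reproducing, and the only arithmetic is a scan count.

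**Step 1: group analysis.** Three statements have to fit together:

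| Place | What it commits to |
|---|---|
| SAP 2.1 | Group analysis of the four subjects not completed |
| SAP 11.1.1, overview | Single-subject level analyses |
| SAP 11.1.1, resting-state fMRI | Group paired t-test, off-therapy against exenatide |

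Part A consists of these four subjects and Part B was cancelled, so the paired t-test has no other group to apply to. The third row conflicts with the first on plain wording, and it goes beyond the second.

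**Step 2: treatment sessions by endpoint in Attachment 11.**

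| Endpoint | Albiglutide session processed? | Comparison stated |
|---|---|---|
| Resting-state BOLD | No; only off-therapy and exenatide named | Off-therapy against exenatide |
| rCBF (pCASL) | Yes; maps for each subject and scan | Off-therapy relative to exenatide |
| Glx and GABA (MRS) | Yes; maps for each subject and session | None for either drug |

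The exclusion of data is therefore confined to BOLD. For pCASL the albiglutide map exists but its comparison is not described. MRS does not favour either drug.

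**Step 3: size of the BOLD omission.** Protocol 4.1 schedules three MRI scans per subject: one off-therapy, one after albiglutide and one after exenatide. Each includes resting-state BOLD. SAP 2.1 gives four completing subjects.

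- Planned resting-state scans: 4 × 3 = 12
- Named for BOLD analysis: 4 × 2 = 8
- Left out: 12 − 8 = 4, all of them the albiglutide scans

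**Step 4: is a reason given?** SAP 2.1 cites early termination and the decision on group analysis. That could explain why no between-drug test is planned. It does not explain why single-subject BOLD processing covers one drug and not the other, or why the only group comparison kept is for exenatide. Termination of Part B does not supply the reason either, because SAP 1, 2.1 and 3.1 all say that Part A was completed as planned.

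**The case against.** The strongest reply on the t-test is that SAP 2.1 may concern only the interim review, since its next sentence draws the conclusion that no interim analyses will be done. On that reading a final group test could survive. This has some force, and it is why the conflict is on plain wording and not beyond argument. But the sentence itself refers to group analysis of the four subjects without limiting it to an interim look, so the plan is at best ambiguous and still needs correcting.

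It can also be said that this is a terminated, exploratory study of four subjects with no pre-specified hypothesis, so nothing inferential is lost. That stands. No error rate or power claim is damaged; the fault is an internal conflict and an unexplained departure from the stated objective.

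Three stronger readings are tempting and are not supported:

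- **Albiglutide was dropped from all imaging.** The per-scan blood-flow maps and per-session metabolite maps rule this out.
- **The BOLD off-therapy comparator was silently changed from the task scan to the resting scan.** Protocol 9.3 names the task data point in its BOLD contrasts, but its own table places off-therapy resting BOLD at the non-task data point. Protocol 7.3.1 takes off-therapy resting data from before any provocation. The protocol is unclear on this, and Attachment 11 is a reasonable reading of it.
- **Most of the protocol's planned contrasts were abandoned.** Protocol 9.4 attaches those contrasts to a final analysis pooling Parts A and B, as appropriate, and that pooled analysis no longer exists. A count would also mix MRS comparisons left unspecified with BOLD comparisons left out.

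**Conclusion.** The point holds in two parts. SAP 2.1 and Attachment 11 disagree, on plain wording, about whether a group analysis of the four subjects takes place. Attachment 11 also leaves the albiglutide session out of resting-state BOLD (4 of 12 planned scans) and omits albiglutide from the stated pCASL comparison, while the primary objective still sets albiglutide against exenatide and no reason is recorded. MRS is not affected.

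The scan count assumes that all four subjects had all three scheduled scans. Whether the albiglutide images are valid is not stated; under SAP 4 the imaging centre determines validity. A reader might infer that the omission was selective reporting. The documents give no reason at all, so they do not support that inference, and an innocent cause such as unusable images remains possible. The point should be fixed before reporting, mainly for consistency and transparency.

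**What to change.** 1. **Reconcile SAP 2.1 with 11.1.1.** Either delete the four-subject group paired t-test, or state in 2.1 that it is kept and why it is for exenatide only.
2. **Add albiglutide to 11.1.1.** Name all three sessions (off-therapy, post-dose albiglutide, post-dose exenatide) for resting-state BOLD, using the single-subject seed-to-voxel method already planned. Extend the pCASL sentence to the albiglutide scan. Report each subject's albiglutide and exenatide results against each other descriptively, without p-values.
3. **If albiglutide was left out deliberately,** for example because images were invalid, give the reason in 2.1 and state that no albiglutide-versus-exenatide conclusion will be drawn for the affected endpoints.

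Items 1 and 3 are wording only. Item 2 costs BOLD processing of up to four further scans that were already scheduled, provided they are valid; the blood-flow maps are already planned for every scan. With four subjects the added output can only be descriptive.

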9.2.2. Sample Size Re-estimation or Adjustment

If subjects prematurely discontinue the study or individual subject technical issues arise, subjects will be replaced at the discretion of the imaging evaluators' judgment in consultation with the Investigator and Sponsor. Subjects will be assigned to the same treatment sequence in order to meet the target number of subjects. Within each phase or part, the randomization of subjects should first be completed before subjects are replaced. Data from subjects who are replaced will be used only for safety analysis.

Issues that may lead to exclusion of data from analysis could include excessive head-motion by the subject during a scan, identifiable artifacts on the brain images arising from problems with the scanner, and issues with the simultaneous physiological recordings (poor signals due to interference, or sensors moving out of position during a scan). Data quality will be iteratively assessed by technical imaging site staff throughout the study in a blinded manner. If some subjects' data is sub-standard and therefore needs to be excluded, additional recruiting and testing may be conducted. Data quality findings will be documented.

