4. ANALYSIS POPULATIONS

Population	Definition / Criteria	Analyses Evaluated
All Screened	
 • All participants who were screened will be considered for this population. This population will be used for summarizing screening status 	
 • Screen failure
Enrolled	
 • All participants who were successfully screened and enrolled for the trial and for whom a record exists on the study database. 	
 • Study population
Safety	
 • Comprise of all subjects who receive at least one dose of study treatment. • This population will be based on the treatment the subject actually received. • This population will include subjects who were replaced due to imaging data being invalid or not evaluable but received study drug. 	
 • Safety
Analysis Set (Randomised)	
 • Comprise of all randomized subjects who receive treatment and with valid imaging data, that will be determined by Martinos. • Subjects who are replaced are excluded from this population. 	
 • Imaging (Mechanism of Action)

NOTES :

- Please refer to Appendix 7: List of Data Displays which details the population to be used for each display being generated.

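### Does the 40-60 grey-matter band for pCASL throw out scans because of their own blood-flow value?

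*SAP*

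**What the plan says.** SAP Attachment 11.1.1 states the band twice. The quality-control overview says the laboratory will calculate rCBF and "ensure values within the gray matter are within normal bounds (40-60 mm/100 g tissue/min". The pCASL paragraph then refers to "adequate data denoted by mean rCBF values over the gray matter within a previously defined normal range", with the same limits. rCBF is on the attachment's list of primary outcomes: "Regional cerebral blood flow (rCBF) (pCASL".

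The overview also provides for "visual inspection of raw brain images for presence of various artifacts" and says the laboratory will "assess head motion correction parameters to ensure that subjects were not moving excessively". On output, the pCASL paragraph says: "These rCBF maps will be calculated for each subject and each scan at the single subject-level".

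Two other places deal with validity. SAP Section 4 limits the imaging Analysis Set to treated, randomised subjects "with valid imaging data, that will be determined by Martinos"; the SAP synopsis calls this a matter of the laboratory's discretion. Protocol 9.2.2 says: "Issues that may lead to exclusion of data from analysis could include excessive head-motion by the subject during a scan". It also names scanner artefacts and faulty physiological recordings, requires quality to be assessed blind, and requires the findings to be documented.

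**The concern.** A quality check should depend on how the data were acquired, not on the answer they give. Here the adequacy criterion is a mean of the quantity that serves as a primary endpoint, while artefacts and motion are already checked by other means. Protocol 9.2.2 says that substandard data need to be excluded, and the Analysis Set requires valid imaging data. Someone who treats inadequate as invalid would drop a scan for its flow value alone.

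Two things would then be at stake. With 4 subjects and two relevant scans each, losing one pair removes 1/4 = 25% of the paired rCBF data. And if exenatide moved blood flow across the whole of grey matter, the pairs that moved most would be the likeliest to leave the band, so the remaining pairs would understate the shift.

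**Working it through.** **1. Is exclusion stated?** The documents give no out-of-band rate, mean, SD or correlation for grey-matter rCBF, so there is no planned figure to reproduce. The texts have to be compared.

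- *MRS paragraph, SAP 11.1.1.* It says which data go forward: those with Cramer-Rao bounds below 40%. That is a gate.
- *pCASL paragraph, SAP 11.1.1.* It has no such sentence. It describes adequate data and then calculates maps for each subject and each scan.
- *SAP Section 4 and synopsis.* Validity is the laboratory's judgement. No numerical cut-off is attached to it.
- *Protocol 9.2.2.* The examples of exclusion are all technical. The list is open-ended, but a flow band is not on it.

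Exclusion on the band is reached only by equating adequate (SAP 11.1.1) with valid (SAP Section 4) and its opposite with substandard (Protocol 9.2.2). Neither document makes that link.

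**2. What would strict exclusion do?** All inputs here are assumptions: grey-matter means normally distributed with mean m and SD s, within-subject correlation r of 0.6 to 0.8, and a pair kept only if both scans lie in 40-60.

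- Share of scans outside the band = 1 - [Φ((60 - m)/s) - Φ((40 - m)/s)].
- Chance of losing at least one of 4 pairs = 1 - K⁴, where K is the bivariate-normal probability that both scans are inside.

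Example with m = 50, s = 5 and no drug effect: share outside = 1 - [Φ(2) - Φ(-2)] = 4.6%. K = 0.920 at r = 0.6 and 0.9286 at r = 0.8. The chance of losing a pair is 1 - 0.920⁴ = 28% or 1 - 0.9286⁴ = 26%. Expected pairs lost are 4 × (1 - K) = 0.32 or 0.29.

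| Assumed SD | Share of scans outside, mean 50 | At least one pair lost, mean 50 | Same, mean 45 or 55 | Global shift of -5 seen in kept pairs, mean 50 |
|---|---|---|---|---|
| 3 | 0.1% | about 1% | 26-29% | about -4.9 |
| 5 | 4.6% | 26-28% | 63-68% | about -4.4 to -4.7 |
| 8 | 21.1% | 76-81% | 87-90% | about -3.3 to -4.0 |
| 10 | 31.7% | 90-93% | 94-96% | about -2.6 to -3.5 |

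The last column comes from 2,000,000 simulated pairs per setting. The answer depends almost wholly on the assumed mean and SD.

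**3. What about a regional effect?** The endpoint is regional flow, and Protocol 9.3 directs the rCBF comparison to nausea-related regions. A regional effect of -5 that covers a fraction w of grey matter moves the global mean by only w × (-5): -0.25 for w = 5% and -1.0 for w = 20%. Over SDs of 3 to 10 at mean 50, the kept pairs show the regional effect as -4.9 to -5.0 for 5% and -4.5 to -5.0 for 20%.

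**4. What analysis would be affected?** SAP 2.1 records that group analysis of the 4 subjects will not be completed, SAP 2.4 has no primary hypothesis, and the pCASL paragraph ends at single-subject maps. No pCASL test, error rate or power figure depends on the band.

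**The case for a change.** The best argument for acting is that the silence is real and one sentence would end it. Adequate is the only pCASL-specific validity language in the SAP. The promise of a map for every scan does not settle the matter either, because flow has to be calculated before the band can be checked. Blind review stops knowing selection by condition, but it does not stop selection on the endpoint's own value. With so few subjects, a reader would want to know whether a missing scan failed technically or was dropped for its mean.

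All of that stands as a description of a gap. It does not show that following the plan gives a wrong result. The band also does something the other checks do not. Protocol 7.3.1 derives flow from an assumed tissue T1, partition coefficient and efficiency, and an implausible global mean is the only listed pCASL-specific sign that this quantification has failed. A scan that passes the motion and artefact checks but has an implausible mean has not thereby been shown to be sound. Replacing the band with labelling and signal criteria would bring in criteria that the documents do not define. The last request is largely met, since Protocol 9.2.2 already requires data-quality findings to be documented.

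**Conclusion.** The concern does not call for a change. The SAP leaves unsaid how an out-of-band pCASL scan is handled, but it states no exclusion rule. The sensible reading is that an out-of-band mean prompts a closer look within the blinded, documented review of Protocol 9.2.2, and an imaging laboratory can be expected to read it so.

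The size of the harm is undetermined. Under strict exclusion, which the documents do not prescribe, the chance of losing a pair runs from about 1% to 96% on inputs that are all assumed, so those figures cannot support any particular severity. Material attenuation needs a shift across all grey matter together with a large between-scan SD; a regional effect, which is what the objective concerns, hardly changes. At most the gap touches descriptive single-subject output from 4 subjects.

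The printed unit (mm per 100 g tissue per minute) is a length where a volume is meant. This is a clerical slip with no bearing on the limits. The conclusion would be different if the SAP made the band an automatic exclusion or built a pCASL group comparison on the scans that passed it.

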3. OBJECTIVE(S) AND ENDPOINT(S)

Objectives	Endpoints
Primary	

 To explore the effect of single dose 50 mg albiglutide compared to single dose 10 µg exenatide on regional brain activity and connectivity associated with nausea in healthy volunteers 	
 Resting-state BOLD signal (fMRI) Regional cerebral blood flow (rCBF) (fMRI-ASL) Glutamate concentration in nausea-associated brain regions (MRS) GABA concentration in nausea-associated brain regions (MRS)
Secondary	

 To evaluate autonomic effects of single dose 50 mg albiglutide compared to single dose 10 µg exenatide To assess safety and tolerability of single dose 50 mg albiglutide and single dose 10 µg exenatide 	
 Heart rate, heart rate variability, respiratory rate, ECG intervals, blood pressure, skin conductance level Vital signs, clinical laboratory tests, adverse events, Nausea ratings scale, GI VAS, and MSAQ
Exploratory	

 To evaluate gastric myoelectrical activity (GMA) of single dose 50 mg albiglutide compared to single dose 10 µg exenatide 	
 GMA: description of frequency region(s) (Bradygastria, Normal, Tachygastria)

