9.3. Data Analysis Considerations

There will be 4 fMRI and 3 MRS data points as shown in the table below:

Treatment Period ^a			Albiglutide	Exenatide
Day Relative to Period Start ^b	1 Off-therapy	1 Off-therapy	8 At T-max	8 At T-max
Visual Nauseogenic Task	No	Yes	No	No
MRI Data Point (DP)	DP1	DP2	DP3	DP4

Treatment Period ^a			Albiglutide	Exenatide
Resting State BOLD fMRI	✓		✓	✓
Nauseogenic task based BOLD fMRI		✓		
ASL	✓		✓	✓
MRS	✓		✓	✓

^a The order of the treatment periods will be randomized.

^b The day is relative to start of the Treatment Period.

For each subject, the Off-therapy Day 1 assessment(s) (DP1 and/or DP2 in table above) during the dosing/imaging sessions will serve as the baseline fMRI assessment.

Nauseogenic task BOLD signal (DP2,) will be assessed only during the off-therapy fMRI session. For the BOLD endpoint, the main contrasts of interest are the differences in the connectivity between albiglutide and off-therapy (DP3-DP2), between Exenatide and off-therapy (DP4-DP2), and between Albiglutide and Exenatide (DP3-DP4).

For resting state analysis rCBF ASL endpoints, the contrasts of interest are the differences DP3-DP1, DP4-DP1, and DP4-DP3. Similarly, for GABA and Glutamate concentrations, the main contrasts of interest are the differences DP3-DP1, DP4-DP1, and DP4-DP3.

The vection-induced nausea will provide a reference to regions of nausea associated brain activity. A group map will be calculated as in the previous Martinos Center study, and regions of interest (ROI) will be defined from the group map. These ROIs will then be used to perform masked comparison analyses for rCBF and MRS (where possible) data between the albiglutide vs exenatide and drug vs no-drug conditions. Such targeted analyses will allow for greater power than whole brain analyses which will need to be more stringently corrected for multiple comparisons.

There will be no imputation for missing data. Subjects who only partially complete the study may be included in some of the analyses where appropriate, depending on which data are available and which are missing.

Summary statistics (including number of subjects, mean, median, min, max, SD, SE) will be reported for continuous variables. The frequency and percentage will be used to summarize categorical variables.

Functional MRI Data

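### The 40% Cramer-Rao cut-off for spectroscopy depends partly on the GABA estimate itself, so it can selectively remove low-GABA voxels and shrink an observed fall in GABA

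*SAP*

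**What the plan says.** GABA concentration measured by MRS is one of the primary endpoints (Protocol section 3; SAP section 2.2).

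SAP 11.1.1 mentions the 40% limit twice. In the quality-control overview it is a check that spectra have adequate signal-to-noise, with "lower bounds values below 40" per cent. In the ¹H-MRS paragraph the bounds, "as reported from the LCModel analysis, will be used to assess the reliability of the major metabolites and adequate SNR", become a retention rule: "CRLBs values less than 40% will be further analyzed". The quantities analysed are Glx and "GABA concentrations, normalized as a ratio with creatine". The MRS outputs are regional differences and a metabolite map for each subject and session.

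Protocol section 9.3 was written for the full study. It says that "for GABA and Glutamate concentrations, the main contrasts of interest are the differences DP3-DP1, DP4-DP1, and DP4-DP3", where DP1 is off-therapy, DP3 albiglutide and DP4 exenatide. On absent values it says: "There will be no imputation for missing data".

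The SAP does not define the denominator of the percentage. It does not say whether the rule applies to a whole spectrum or to each metabolite, and it gives no expected bound for GABA. It has no common voxel mask, no count of exclusions by session, and no display that keeps all values.

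**The concern.** A Cramer-Rao bound is a lower limit on the standard deviation of a fitted concentration. Expressed as a percentage of the estimate, it combines two things: spectral noise in the numerator and the amount of metabolite in the denominator. Two spectra of equal quality can fall on opposite sides of 40% only because one contains less GABA.

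If a drug lowers GABA, more voxels fail on drug than off therapy, and those that survive are the higher estimates. The sessions of one subject then cover different voxels, and the observed fall is too small. Because nothing is imputed and exclusions are not counted, the reader of the maps could not see that this had happened.

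**Working it through.** The plan gives no derivation of the 40% limit and no sample-size or power figure for MRS, so there is no figure of its own to reproduce. The check models the rule directly.

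**Inputs from the documents:** cut-off 40% (SAP 11.1.1); within-subject comparison of sessions and no imputation (Protocol 9.3).

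**Assumptions, not in the documents:** the percentage is relative to the estimate and is applied to GABA itself; the estimate is normal around the true value with SD equal to the absolute bound s; s is the same in both scans; the off-therapy bound lies between 10% and 40%; the true fall is 20% (10% and 30% also run). The creatine ratio is not modelled.

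**Step 1, the rule restated.** s / estimate < 0.40 is the same as estimate > s / 0.40 = 2.5 s.

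**Step 2, formulas in units of s.** Off-therapy mean μ₀ = 1 / bound; on-drug mean μ₁ = 0.8 μ₀. Share kept = Φ(μ − 2.5). Mean of kept values = μ + φ(μ − 2.5) / Φ(μ − 2.5).

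**Step 3, off-therapy bound of 30%.**
- Off therapy: μ₀ = 3.333; kept Φ(0.833) = 80%; mean kept 3.687.
- On drug: μ₁ = 2.667; kept Φ(0.167) = 57%; mean kept 3.362.
- Observed fall: 1 − 3.362 / 3.687 = 8.8%, against a true 20%.

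**Step 4, the range for a true 20% fall.**

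| Off-therapy bound | Kept off therapy | Kept on drug | Observed fall |
|---|---|---|---|
| 10% | 100% | 100% | 20.0% |
| 15% | 100% | 100% | 19.9% |
| 20% | 99% | 93% | 17.5% |
| 25% | 93% | 76% | 12.7% |
| 30% | 80% | 57% | 8.8% |
| 35% | 64% | 42% | 6.3% |
| 40% | 50% | 31% | 4.8% |

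At bounds of 20%, 25% and 30%, a true 10% fall appears as 9.2%, 6.9% and 4.8%, and a true 30% fall as 24.5%, 17.4% and 12.1%.

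**Step 5, spread in true GABA.** The table assumes none. With an SD of 0.20 (off-therapy mean = 1), the observed falls at bounds of 15%, 20%, 25% and 30% are 17.9%, 14.6%, 11.0% and 8.1%. The point at which the bias becomes negligible therefore moves down somewhat.

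**Step 6, requiring both scans to pass the 40% rule.** A simulation of 2,000,000 pairs (SD 0.10 between subjects, true fall 20%) recovers 0.99, 0.88, 0.70 and 0.54 of the true difference at bounds of 15%, 20%, 25% and 30%. A common mask built from the same percentage filter does not remove the bias.

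**Step 7, without estimation noise.** A fall alone pushes a value to the limit only if the off-therapy bound is at least 40% × (1 − fall): 36%, 32% and 28% for falls of 10%, 20% and 30%.

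**The case against.** Four objections have force.

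- **The rule does measure quality.** The numerator is fitting error, so a noisy spectrum with normal GABA also fails, as intended. A reader might infer that the rule selects on the outcome instead of on spectral quality. It does both, and only the first part is a problem.
- **The unit of application is assumed.** The overview speaks of spectra, and the MRS paragraph of major metabolites. If whole spectra were accepted on the fits of other metabolites, selection on GABA need not arise. That reading is possible. The retention sentence fits a metabolite-by-metabolite filter more naturally, but the SAP should say which applies.
- **Nothing places this study where the bias matters.** A reader might infer that a 40% limit means GABA bounds of 20–40% are expected. A ceiling gives the worst acceptable value, not the typical one. The documents therefore do not support saying that a GABA fall is masked, or that values are inflated in every condition.
- **There is no formal estimate to bias.** SAP section 2.1 records four completers in Part A, cancellation of Part B, and a decision against group analysis. No hypothesis is specified, and the only group test in the attachment is for resting-state fMRI. A reader might infer a biased treatment effect from the contrasts in Protocol 9.3, but the SAP plans no such MRS test. It still promises regional differences and session maps, and those are exposed.

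Keeping noisier values is also a real trade-off when maps are read subject by subject.

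**Conclusion.** The concern holds in conditional form. On the natural reading, the cut-off depends partly on the GABA estimate, and the distortion of a fall runs one way, toward zero. For a true 20% fall it ranges from nothing material at an off-therapy bound of 15% or lower to a loss of more than half of the fall at 30% (8.8% observed). This rests on normal error, equal noise in the two scans and little spread in true GABA. The actual size cannot be stated from the documents.

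The consequence is limited to single-subject maps with selectively missing voxels and to descriptive session differences in a primary endpoint. It is worth correcting because the plan contains nothing that would offset or reveal it.

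**What to change.** In SAP 11.1.1:

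1. Replace the 40% cut-off as the acceptance rule with criteria that do not depend on GABA or Glx: spectral signal-to-noise, linewidth and the fit quality of creatine. Fix the limits while the imaging evaluators are blinded; Protocol 6.4 and 9.2.2 already provide for blinded evaluators and blinded quality assessment.
2. Use one voxel mask per subject, made of the voxels that pass these criteria in every scan compared.
3. Keep all GABA and Glx estimates inside the mask, and report the absolute bound (percentage bound × estimate) with each.
4. Report the number of voxels excluded by session.
5. Show the map under the 40% filter as a sensitivity display, stating the denominator of the percentage and whether the filter works by spectrum or by metabolite.

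The cost is revised SAP wording and a change to the post-processing script; the absolute bound follows from quantities the fit already reports. The downside is that some noisier GABA values remain in the maps, which the reported bounds make visible.
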